6.1 Statistical Analysis

6.2 General

A detailed statistical analysis plan will be finalized prior to performing any analyses to expand upon the statistical methods presented below. Summary tables will summarize data for all subjects together.

6.3 Sample Size Determination

No pre-specified sample size calculations were performed for this post-market, prospective, non-randomized, single-arm, multicenter study.

6.4 Analysis Populations

Intent-To-Treat (ITT): subjects enrolled into the study.

Modified ITT (MITT): ITT subjects who underwent the ablation procedure.

6.5 Demographics and Other Subject Characteristics

Subject demographics and pre-treatment characteristics will be summarized for the ITT population.

6.6 Effectiveness Analysis

Effectiveness analyses will be done for the MITT population.

6.5.1 Primary Endpoint

The primary endpoint is dose response immediately post-procedure (for each target tumor) and is defined as the percentage change from the predicted outcome to the actual outcome. The percentage change (calculated as $100*(A-P)/P$) will be calculated for each target tumor, where P=predicted and A=actual. The percentage change will be calculated for each tumor for the following measurements:

- Ablation zone width (X)
- Ablation zone height (Y)
- Ablation zone depth (Z)
- Ablation zone volume
- Ablation zone shape

For each of the above measurements, the percentage change for all tumors will be summarized. Summary will also be done by tumor type.

The predicted values will come from the Procedure Planning Application and the actual values will come from the CT imaging.

6.5.2 Secondary Endpoints

The number and percentage of tumors which achieve complete tumor ablation, incomplete tumor ablation (delayed necrosis) and incomplete tumor ablation (positive margin) (both overall and according to tumor type) will be presented. Ablation will be assessed using histology. A 95% exact binomial confidence interval will be calculated for each response.

6.6 Safety Analysis

Safety analyses will be done for the MITT population.

6.6.1 Exposure

The dosing information (time, power) will be listed by subject.

6.6.2 Adverse Events & Complications

Tables to summarize the incidence rates will be created for each of the following groups:

- Adverse events
- Serious adverse events
- Adverse events leading to premature discontinuation
- Adverse device effects (ADE)
- Serious adverse device effects (SADE)
- Unanticipated serious adverse device effects (USADE)
- Adverse events by intensity
- Adverse events by relationship to study product administration

Adverse events that led to premature discontinuation from the study will be listed. Serious adverse events, SADE and USADE will also be listed.

6.7 Interim Analyses

An interim analysis will be conducted once the first 15 tumors are ablated (preferably representative samples from each site).

6.8 Handling of Missing Data

Missing data rules will be specified in the detailed statistical analysis plan.

7.1 Risk/Benefit Analysis

The purpose of this study is to create and evaluate an ablation zone created in patients already scheduled for surgical resection of metastatic or primary lung disease per standard practice. The ablation procedure is not intended to treat the target tumor.

Since the Emprint™ Ablation system is similar in technology and indication to the existing MWA systems currently marketed in the U.S., EU and ROW, the potential harms associated with the Emprint™ Ablation System are the same as those presented in the literature and reported complaints. More specifically, the current hazard analysis for the Emprint™ Ablation system identified the following lung specific potential harms related to use of the Emprint™ Ablation System:

- Pneumothorax
- Skin Burn
- Unintended Parenchymal Ablation, defined as lung parenchymal ablation extended > 1 cm beyond predetermined volume of ablation safety margins
- Tissue Tear
- Microwave/Thermal Burn causing damage to extrapulmonary structure (*e.g.*, pleural burn, Diaphragmatic Paresis or perforation, Vessel Thrombosis, Mediastinal burn)
- Bleeding (*e.g.*, Hemorrhage, Hemothorax, Hematoma, Hemoptysis)
- Infection (*e.g.*, Abscess, Pneumopathy)
- Procedural Delay (*e.g.* delayed or canceled surgery)
- Foreign Object in Body

The risk analysis assumes the system is operated by quality, properly trained personnel. The overall residual risk after design risk mitigation strategies and/or design control was deemed acceptable in the Risk Management Report for the Emprint™ Ablation System.

7.2 Anticipated Risks Associated with Lung Tumor Ablation Reported in Literature and by Investigators

Based on the evidence summarized in Section 3.2, potential risks associated with lung tumor ablation with the Emprint™ Ablation System include but are not limited to:

- Pneumothorax (9,10,12)
 - Mild severity (reported incidence: 4.6% - 27%)
 - Moderate or severe severity (reported incidence: 3.9% -12%)
- Pleural Effusion
- Skin burns (reported incidence: 0.8 % - 4.3%) (9,10,16)
- Acute respiratory distress (reported incidence: 2%) (9)
- Self-limiting hemoptysis (reported incidence: 4.6% – 7.25%) (9,10,12,14)
- Hemorrhage requiring additional intervention treatment (reported incidence: 1-2%) (investigator experience)
- Empyema development (reported incidence: <5%) (17)
- Post-ablation syndrome, defined as productive cough with or without minor hemoptysis, residual soreness in the treated area, and fever occurring several days post-ablation (reported incidence: 2%) (9)
- Post-procedural pain (reported incidence: 2%) (9)
- Slight risk of bleeding from placement of the microwave ablation antenna
- Insufficient coagulation (single report in MAUDE database)
- Nerve Injury (*e.g.*, stallate ganglion, intercostal and phrenic nerves)

Oncologic and surgical principles should not be compromised by the addition of tumor ablation to the surgical resection procedure. The tumor will be completely excised and the single-use antenna will not be used again in any living tissue. Thus, this study protocol does not impart any risk of spreading tumor cells.

Reproductive and developmental toxicology studies in animals to evaluate the potential for AEs on reproductive ability and effects on the embryo/fetus have not been conducted. Subjects who are pregnant (documented by a positive pregnancy test) or are actively breast-feeding are excluded per study protocol.

7.3 Risks Associated with Additional Radiation Exposure for Study-Related CT Imaging

There are risks associated with the use of CT. The main risks are those associated with the increased possibility of cancer induction from x-ray radiation exposure. Normally, an individual may be exposed to approximately 3 millisieverts of radiation each year just from background environmental radiation, such as radon and cosmic rays. In higher elevation areas an individual's background exposure can be as high as 10 millisieverts per year. The expected additional exposure due to the CT procedures in this study would be in the range of 12 to 30 millisieverts.

The probability for absorbed x-rays to induce cancer or heritable mutations leading to genetically associated diseases in offspring is thought to be very small for radiation doses of the magnitude that are associated with CT procedures and for any one person the risk of radiation-induced cancer is much smaller than the natural risk of cancer. However, an individual's risk of harmful effects may increase if they are exposed to additional procedures that involve radiation such as x-rays or if additional CT scans are required for care.

7.4 Risks Associated with Study Procedure

There is a potential for longer procedure time; however, because other aspects of the planned surgical resection procedure can be conducted during the ablation, the addition of ablation to the procedure is unlikely to cause a significant increase in procedure time.

Additionally, there is a risk that based on the length and execution of the ablation procedure, the standard of care surgical resection may need to be rescheduled to the day after the ablation procedure, resulting in an overnight hospital stay for the study subject. This is a small risk, however, if this occurs, all costs related to the additional overnight hospital stay will be incurred by the Sponsor.

7.5 Potential Benefits to the Subject

Because this study will be conducted in patients already scheduled for surgical resection of metastatic or primary lung tumors, the study protocol will not impart significant benefits beyond the benefit of lung resection alone.

If the results of this study are favorable, further studies may be justified to evaluate the potential for improved standard of care using microwave ablation technology in inoperable lung tumors and patients.

8.1 Adverse Events, Complications, and Product Complaints

Since this product is a legally marketed product, all SAE's regardless of cause, device and/or ablation procedure related AEs or complications and product complaints will be reported to Covidien Post Market Vigilance for documentation and investigation according to CI-007D.

8.2 Adverse Event (AE)

An Adverse Event is any untoward medical occurrence, unintended disease or injury, or untoward clinical signs (including abnormal laboratory findings) in subjects, users or other persons, whether or not related to the medical device.

Adverse events will be collected starting from the initial administration of anesthesia to the patient until conclusion of the first post-operative follow-up visit. All enrolled subjects will be evaluated for Adverse Events regardless of whether or not the subject received the planned ablation and resection.

It should be noted the risks identified above are similar to those noted for standard lung resection. In some cases, it will be impossible to differentiate surgery induced AE's from ablation induced AEs, specifically for AE's that occur after surgery. This should be noted as a limitation in quantifying device and/or ablation procedure related AEs .

8.3 Serious Adverse Event (SAE)

A Serious Adverse Event is an adverse event that has

- a) led to death,
- b) led to serious deterioration in the health of the subject, that either resulted in
 - 1) a life-threatening illness or injury, or
 - 2) a permanent impairment of a body structure or a body function, or
 - 3) in-patient or prolonged hospitalization, or
 - 4) medical or surgical intervention to prevent life-threatening illness or injury or permanent impairment to a body structure or a body function,

NOTE: Planned hospitalization for a pre-existing condition, or a procedure required by the clinical investigational plan, without serious deterioration in health, is not considered a serious adverse event.

8.4 Adverse Device Effect (ADE)

An Adverse Device Effect is an adverse event related to the use of a medical device.

This definition includes adverse events resulting from insufficient or inadequate instructions for use, deployment, installation, or operation, or any malfunction of the medical device.

This definition includes any event resulting from use error or from intentional misuse of the medical device.

8.5 Serious Adverse Device Effect (SADE)

A Serious Adverse Device Effect is an adverse device effect that has resulted in any of the consequences characteristic of a serious adverse event.

8.6 Unanticipated Serious Adverse Device Effect (USADE)

An Unanticipated Serious Adverse Device Effect is a serious adverse device effect which by its nature, incidence, severity, or outcome has not been identified in the current version of the risk analysis report.

8.7 Definitions of Specific Adverse Events

This list is not meant to be all inclusive but representative of specific adverse events relevant to the ablation procedure and/or outcome.

- Pneumothorax, defined as clinically significant: expanding and requiring a chest tube insertion or non-clinically significant: radiologically apparent in a non-symptomatic patient
 - The incidence of non-clinically significant pneumothoraxes will be collected as a safety endpoint only and will be used to determine trends for follow on studies. Clinically significant pneumothoraxes will be reported as AE's if a chest tube is needed prior to the surgical intervention.
- Pleural Effusion, defined as the accumulation of excess fluid in the pleural cavity after the ablation procedure and prior to the initiation of the surgical procedure
- Bleeding – an outcome of the failure to achieve or maintain hemostasis that results in
 - Hematoma
 - Hemorrhage (includes parenchymal pulmonary hemorrhage, hemothorax, and hemoptysis), defined by a change in vital signs sometimes requiring resuscitation

Bleeding will be assessed after the ablation procedure and prior to initiation of the surgical resection and will be evaluated based on the following CTCAEv.4 definitions:

HEMORRHAGE/BLEEDING							Page 1 of 4
Adverse Event	Short Name	Grade					
		1	2	3	4	5	
Hematoma	Hematoma	Minimal symptoms, invasive intervention not indicated	Minimally invasive evacuation or aspiration indicated	Transfusion, interventional radiology, or operative intervention indicated	Life-threatening consequences; major urgent intervention indicated	Death	
REMARK: Hematoma refers to extravasation at wound or operative site or secondary to other intervention. Transfusion implies pRBC. ALSO CONSIDER: Fibrinogen; INR (International Normalized Ratio of prothrombin time); Platelets; PTT (Partial Thromboplastin Time).							
Hemorrhage/bleeding associated with surgery, intra-operative or postoperative	Hemorrhage with surgery	—	—	Requiring transfusion of 2 units non-autologous (10 cc/kg for pediatrics) pRBCs beyond protocol specification; postoperative interventional radiology, endoscopic, or operative intervention indicated	Life-threatening consequences	Death	
REMARK: Postoperative period is defined as ≤72 hours after surgery. Verify protocol-specific acceptable guidelines regarding pRBC transfusion. ALSO CONSIDER: Fibrinogen; INR (International Normalized Ratio of prothrombin time); Platelets; PTT (Partial Thromboplastin Time).							
Hemorrhage, CNS	CNS hemorrhage	Asymptomatic, radiographic findings only	Medical intervention indicated	Ventriculostomy, ICP monitoring, intraventricular thrombolysis, or operative intervention indicated	Life-threatening consequences; neurologic deficit or disability	Death	
ALSO CONSIDER: Fibrinogen; INR (International Normalized Ratio of prothrombin time); Platelets; PTT (Partial Thromboplastin Time).							

- Device Deficiencies including but not limited to:
 - Device components left inside the subject – any part of the antenna breaking and dislodging in the patient
 - Generator malfunction leading to premature termination of ablation cycle
- Unintended Parenchymal Ablation, defined as lung parenchymal ablation extended > 1 cm beyond predetermined volume of ablation safety margins
- Microwave/Thermal Burn causing damage to extrapulmonary structures (*e.g.*, pleural burn, Diaphragmatic Paresis or perforation, Vessel Thrombosis, Mediastinal burn)
 - Grade 1: minimal symptoms, no intervention
 - Grade 2: medical intervention, debridement
 - Grade 3: moderate/major debridement, reconstruction
- Nerve Injury (*e.g.* stallate ganglion, intercostal and phrenic nerves), defined as one of the following:
 - Neuropathic pain or dysesthesia in the distribution of an intercostal nerve adjacent to the ablation zone
 - Horner’s Syndrome (proptosis, meiosis and anhidrosis of the ipsilateral eye) related to thermal injury of a high upper lobe tumor situated medially abutting the paraspinal region
 - New paralysis of the ipsilateral hemidiaphragm related to thermal injury of the phrenic nerve
- Musculoskeletal Fracture- if immobilization needed or operative intervention is required
- Soft Tissue Tear resulting in partial resection of injured area
- Allergic/Toxic Reaction

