5.5.1 Inclusion Criteria

- Subject or authorized representative has provided informed consent
- Subject is ≥ 18 years of age

- At least one pulmonary metastasis ≤ 3.0 cm in maximum diameter resulting from distant primary cancers or one primary lung cancer ≤ 3.0 cm in maximum diameter
- Subject has been confirmed by a thoracic surgeon to be a surgical candidate for resection of the tumor targeted for ablation
- Subject is willing and able to comply with all aspects of the treatment and evaluation schedule
- ≥ 1 cm of tumor-free lung parenchyma between target tumor and pleura or fissure

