Once antenna placement has been verified, the Emprint™ generator will be set by clinician to deliver the prescribed dose based on target tumor size plus a 0.5 cm margin and physician experience. Once the generator settings have been verified, the ablation will be initiated either by the investigator, using a foot switch, or radiology technician / scrub nurse, using the user interface on the generator.

Once the ablation is complete, the antenna will remain in place and the third CT image will be taken to evaluate the characteristics of the resulting ablation zone. The antenna will then be removed and the final CT image will be taken and will be used to identify adverse events that may have occurred during the ablation procedure.

Once the final CT image has been acquired, the ablation zone will be resected as scheduled, by the thoracic surgeon per standard surgical practice. The resected tissue will then be sent to the on-site pathology laboratory for sample preparation. The prepared samples will be sent to a core laboratory for histologic analyses.

If complications arise due to the microwave ablation, termination of the session will be determined at the discretion of the investigator according to the severity of the event and the extent of the intervention required.

CT imaging using a multidetector row helical CT scanner (minimum 8 detector) will be employed four times during the patients' enrollment in the study. The first three scans will be higher resolution to accurately measure target tumor size, antenna placement, and the ablation zone. The final CT will be a low dose scan to assess the presence of bleeding or pneumothorax that occurred during the ablation. Scan parameters for the first three scans will be as follows:

- Detector collimation – 1.5 mm or less
- Pitch < 1
- 120kVp
- Reference 100-140 mA (dependent upon body habitus). Auto mA may be left on, but all other dose reduction should be turned off.
- Scans will be performed with a breath hold at end inspiration with arms elevated over head if possible.
- No IV contrast.
- Images for 3D processing will be reconstructed at 1.5 mm with a 20% overlap using a standard kernel.

Scan parameters for the fourth low dose scan will be as follows:

- Detector collimation – 2.5 mm or less
- 120kVp

- Reference 40-80 mA (dependent upon body habitus)
- Scans will be performed with a breath hold at end inspiration with arms elevated over head if possible.
- No IV contrast.

1. Pre-procedure Scan

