A Pre-procedure CT scan is only required on the day of the procedure if the standard of care CT scan was performed more than 30 days prior to the procedure date.

Scan volume should extend from the clavicles through the lung bases.

CT imaging either acquired the day of the procedure or up to 30 days prior will be used by Intrinsic, to confirm the location of the target tumor. More specifically, all tumors will be measured in three dimensions (maximum dimension, maximum perpendicular dimension, and third perpendicular dimension) on pre-procedure CT images by the imaging core laboratory. Tumor volume will also be directly measured with volumetric post-processing. Maximum transverse axial and perpendicular axial measurements will also be obtained to allow for comparison of tumor sizes with tumor sizes as recorded in most standard oncology trials.

These images and required reconstructions must be sent to Intrinsic Imaging.

2. Intra-procedural Scan

When the antenna is in its final location prior to commencing ablation, the intra-procedural CT will be obtained. Scan volume should extend from 5cm above the superior margin of the tumor to 5cm below the inferior margin of the tumor to help minimize unnecessary imaging of tissue outside the area of immediate procedural concern.

Intrinsic Imaging will use the image(s) of final placement of the antenna to evaluate technical accuracy, which is defined as correct positioning of antenna within the tumor. These data will specifically be used to evaluate any occurrence of incomplete ablation.

These images and required reconstructions must be sent to Intrinsic Imaging.

3. Post Procedure Scan (Antenna in Place)

Scan volume should extend from the clavicles through the lung bases. This CT scan will be obtained once the ablation is complete but with the antenna still in place. This Post-procedural imaging will be used to assess dose response.

These images and required reconstructions must be sent to Intrinsic Imaging.

4. Post Procedure Scan (Antenna Removed)

Scan volume should extend from the clavicles through the lung bases.

This CT scan will be obtained to identify and evaluate acute adverse events that may have occurred during the ablation procedure.

Anesthesia

Anesthesia use will be determined by each site per standard of care and will be administered after ablation planning has occurred.

Ablation Procedure

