8.11 Adverse Event Recording and Reporting

[figure not shown]
In addition to the adverse event reporting required for post market device reporting, adverse events occurring during the ablation procedure and/or attributed to the ablation procedure will be recorded in an AE CRF and reported in clinical study reports.

Assessment of the occurrence of an AE will be based on changes in the subject's physical examination, laboratory results and/or signs and symptoms. Adverse events will be monitored until conclusion of the first post-operative follow-up visit unless the Investigator determines the event is related to the device or ablation procedure, in which case they will be monitored until resolution if possible. Medical care will be provided, as defined in the informed consent, for any device or ablation procedure related AEduring study participation. Adverse events will be collected on an AE eCRF and applicable source documentation. To the extent possible, the event to be recorded and reported is the event diagnosis as opposed to event symptoms (e.g., fever, chills, nausea and vomiting in the presence of a clinically diagnosed infection is to be reported as infection only). For the purposes of this protocol, only those AEs occurring after initial administration of anesthesia will be recorded.

The following should not be considered an AE:

- A condition requiring a preplanned procedure unless the condition worsened since screening
- A preexisting condition found as a result of screening, unless the condition has worsened since the screening visit, and is noted on the day of the procedure

All AEs observed during the ablation procedure for this study, regardless of severity or relationship to the device will be recorded on the appropriate CRF and reported in clinical study reports. Only device and/or ablation procedure related AE's deemed possible, probable, or definitely related will be reported during the surgical resection. To ensure reported events can be attributed to the device and/or ablation procedure, it is strongly recommended that a safety evaluation be performed immediate post-ablation procedure to capture acute events and again prior to the scheduled surgical resection.

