### 7.7.1. Planning Application

Planning application characteristics:

- Axial two-dimensional measurement - maximum axial length
- Axial two-dimensional measurement - perpendicular axial length associated within maximum axial length
- Planned antenna point of entry (intercostal space)
- Planned approach
- Planned ablation time
- Planned ablation power
- Planned tip distance
- Planned insertion depth
- Target tumor width (X)
- Target tumor height (Y)
- Target tumor depth (Z)
- Calculated target tumor volume from planning application
- Predicted ablation zone width (X)
- Predicted ablation zone height (Y)
- Predicted ablation zone depth (Z)
- Predicted ablation zone volume
- Predicted minimum margin
- Predicted maximum margin

This document is electronically controlled. Printed copies are considered uncontrolled.

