**Confidential**

- Presence of cavitation
- Maximum margin
- Minimum margin
- Location of areas with margins less than 0.5mm

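### Unintended parenchymal ablation is defined by how far the zone exceeds the plan, but no step assigns its detection, so a reported zero would not mean every tumor was checked

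*Protocol*

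**What the plan says.** **Definition.** Protocol 8.7 includes among its specific adverse events "Unintended Parenchymal Ablation, defined as lung parenchymal ablation extended > 1 cm beyond predetermined volume of ablation safety margins". Section 7.1 lists the same event, defined the same way, as a lung-specific harm from the hazard analysis.

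**Detection.** Section 8.11 bases the judgment that an AE has occurred on changes in "physical examination, laboratory results and/or signs and symptoms". It also has a broad recording rule: "All AEs observed during the ablation procedure for this study, regardless of severity or relationship to the device will be recorded".

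**Imaging.** Section 5.7.5 describes four CT scans. Scan 3, taken with the antenna still in place, is for dose response and goes to the imaging core lab. Scan 4, taken after the antenna is out, has a general purpose, "This CT scan will be obtained to identify and evaluate acute adverse events that may have occurred during the ablation procedure", and a narrower one, "The final CT will be a low dose scan to assess the presence of bleeding or pneumothorax that occurred during the ablation". The instruction to send images to the core lab appears for scans 1 to 3 and not for scan 4.

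**Analysis.** The SAP summarizes "Predicted maximum margin" among planning characteristics (7.7.1) and "Maximum margin" among CT imaging characteristics (7.7.3). It defines no difference between the two and does not use the 1 cm threshold. SAP 7.10 tabulates reported AEs by system organ class and preferred term. None of the eight AE groups in protocol 6.6.2 is defined by zone extent.

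**The concern.** Whether this event occurred can be settled only by laying the achieved zone against the planned one. Examination, laboratory values and symptoms do not show how far a zone extends within lung.

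The protocol is more explicit for other events. Section 8.7 has a category of pneumothorax that is purely radiological, and it says when bleeding is to be assessed. The assessments table (5.7.1) has rows for pneumothorax, hemorrhage and thermal injury, but none for this event. Resection is meant to follow immediately or the same day, and within 36 hours at most without a deviation (5.7.6). A silent overshoot may therefore be removed before it causes any sign.

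What is at stake is the meaning of the AE table. A zero for this event would be read as no overshoot, when it may mean only that nobody made the comparison. That error favors the device.

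**Working it through.** **1. Tracing the event from definition to table**

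| Step | Place | Provision for this event |
|---|---|---|
| Definition | Protocol 8.7, 7.1 | Geometric, more than 1 cm beyond plan |
| Assessment rule | Protocol 8.11 | Imaging not named |
| Scan showing the zone | Protocol 5.7.5, scan 3 | Assigned to dose response |
| Scan read for AEs | Protocol 5.7.5, scan 4 | Acute AEs in general; bleeding and pneumothorax in particular; zone extent not named |
| Plan and result data | SAP 7.7.1, 7.7.3 | Maximum margins held as separate descriptive rows |
| AE tables | SAP 7.10, protocol 6.6.2 | Reported AEs only; no derived flag |

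No row joins the plan to the result for safety purposes.

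**2. What a reported zero would be worth**

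The documents give no expected rate for this event and no sample size calculation, so there is no stated figure to reproduce. Inputs: n = 30, the enrollment maximum, taken as one tumor per subject (assumption); p, the true overshoot rate (assumed); s, the share of overshoots recorded as AEs (assumed).

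P(zero reported) = (1 − p·s)^30

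| p | s = 0 | s = 0.25 | s = 0.5 | s = 1 |
|---|---|---|---|---|
| 5% | 1.000 | 0.686 | 0.468 | 0.215 |
| 10% | 1.000 | 0.468 | 0.215 | 0.042 |
| 20% | 1.000 | 0.215 | 0.042 | 0.001 |

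The exact two-sided 95% upper limit for 0/30 is 1 − 0.025^(1/30) = 11.6%. For 0/15, the size of the interim analysis, it is 1 − 0.025^(1/15) = 21.8%. Both limits hold only if every tumor was assessed (s = 1).

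**3. What the primary endpoint would show**

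Percentage change is 100·(A − P)/P. Assume a spherical planned zone of tumor diameter plus 2 × 0.5 cm, the minimum margin in 5.7.5.

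- 3 cm tumor, uniform 1 cm overshoot: 4 to 6 cm, so +50% in diameter and 100·((6/4)³ − 1) = +237.5% in volume.
- 1 cm tumor, uniform 1 cm overshoot: 2 to 4 cm, so +100% in diameter and 100·((4/2)³ − 1) = +700% in volume.
- Overshoot on one side only: 1/4 = +25% or 1/2 = +50% on that axis.
- Zone of the planned size displaced by more than 1 cm: 0% change in width, height, depth, volume and shape, although the definition is met.

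The reported ranges can therefore expose a large uniform overshoot, but they do not count the event and can miss a displaced zone.

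**4. What the maximum margins would show**

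At the place where the actual margin is largest, the planned margin cannot exceed the predicted maximum. An actual-minus-predicted difference above 1 cm therefore shows more than 1 cm of overshoot in that direction. The converse fails. Suppose planned margins are 1.5 cm on one side and 0.5 cm on the other, and achieved margins are 1.5 and 1.7 cm. The true overshoot is 1.7 − 0.5 = 1.2 cm, but the difference of maxima is 1.7 − 1.5 = 0.2 cm. The difference gives a lower bound on the number of events.

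**5. Tumors near the pleura**

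Eligibility requires "≥ 1 cm of tumor-free lung parenchyma between target tumor and pleura or fissure". At the minimum distance, with a 0.5 cm planned margin, 1.0 − 0.5 = 0.5 cm of lung remains toward the pleura, less than the threshold. With that margin, the threshold can be passed in that direction only for a tumor more than 0.5 + 1.0 = 1.5 cm from the pleura.

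**The case against.** A reader might infer that the event cannot be found at all, or that overshoot is never measured. The documents support neither.

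- Scan 4 is a route from imaging to AEs, and its general description is not limited to bleeding and pneumothorax.
- The procedure record includes zone diameter and volume on post-procedure CT (5.7.5), and the investigator has already captured the predicted zone in a snapshot.
- All AEs observed during ablation are recorded, ablation-specific complications are collected (5.7.1), and a safety evaluation straight after ablation is strongly recommended (8.11).
- Grade 1 in section 8.8 covers findings that are diagnostic only.
- An interventional radiologist serves as independent medical monitor and adjudicates pre-specified events (10.1).
- Planned against achieved size is the primary endpoint, measured by the core lab and summarized with ranges (SAP 7.9.1).

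In addition, the Safety Plan and the monitor's charter are not among the documents and may cover part of this. The study is descriptive, and the whole zone is meant to be resected.

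All of this stands, and it shows that an overshoot may be noticed. None of these provisions requires a plan-against-result check for safety on each tumor, applies the 1 cm threshold, or supplies a denominator of tumors checked.

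**Conclusion.** The point holds as a gap in detection and counting: the event has no assigned method or assessor, and the AE tables draw only on what is reported. At an assumed 10% true rate in 30 tumors, the chance of a zero count runs from 0.042 with complete ascertainment to 1.000 with none. Where the study would fall in that range cannot be known from the documents. The primary endpoint is unaffected. This is an inexpensive improvement to the safety reporting.

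Two further readings go too far. A reader might take this as the protocol's only signal of over-treatment, but thermal burn to extrapulmonary structures and nerve injury, both in 8.7, can also follow over-extension. A reader might also conclude that the definition can never be met toward a pleura or fissure. Lung continues beyond a fissure, and toward the pleura the limit applies only to tumors near the eligibility minimum. All that follows is that some overshoot toward the pleura may stay below the threshold, which is a reason to list the difference for each tumor.

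The conclusion assumes that the predetermined volume in 8.7 means the planned zone in the snapshot; the protocol does not tie the term to a named variable.

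**What to change.** State in protocol 8.7 and SAP 7.10 that this event is assessed for every ablated tumor from scan 3 against the planning snapshot, using the protocol's existing threshold of more than 1 cm, and name the core lab as assessor.

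- At minimum, derive actual minus predicted maximum margin per tumor from data already collected, flag differences above 1 cm, and list the difference for every tumor.
- State that the flagged count is a lower bound, because the two maxima may lie at different places. Use a location-matched comparison where the existing core-lab read allows it.
- Tabulate flagged over assessable tumors beside the site-reported AEs, and pass flagged cases to the medical monitor.
- Say which variable represents the predetermined volume in the definition.

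The minimum version costs one derived variable, one table row and one listing. A location-matched comparison needs more core-lab work, since plan and result images must be aligned. The reported overshoot count may come out higher than site reporting alone would give.
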